Rationale: The development of a machine learning algorithm that predicts American Society of Anesthesiologist-Physical Status (ASA-PS) based on preoperative variables would not only improve clinical decision-making in patient risk stratification but also offer a more reliable tool for administrative and regulatory uses. Therefore, the development of such a machine learning tool presents a significant opportunity to advance both the science and practice of perioperative care. Incorporating medication use into the algorithm could further enhance its predictive power, as it is closely linked to systemic disease. This addition could help refine the ASA-PS classification, making it an even more valuable tool in the clinical setting.

Objective(s): To develop a machine learning algorithm that can predict the American Society of Anesthesiologists Physical Score (ASA-PS) I-IV based on gender, age, BMI, standard health questionnaire and medication use (ATC) and determine its performance.

Study type: A retrospective cohort study of routinely collected health data of patients who had surgery in the Erasmus MC.

Study population: All patients, 18 years or older, who underwent elective surgery in the Erasmus MC since the introduction of HiX and who have had a preoperative anesthesiological consultation.

Methods: Multiple machine learning algorithms predicting ASA-PS using age, sex, BMI, health questionnaires and ATC codes of used medication will be developed, validated and evaluated.

Burden and risks: none

Recruitment and consent: Based on art. 24 of the “Uitvoeringswet AVG”, this research will be performed under the exception consent:

- Obtaining informed consent of all patients in this database (>90.000 patients) demands an unreasonable effort.
- The study serves a general purpose (triage of patients for personalized preoperative screening)
- Data that is processed is stored in pseudonymized format and cannot lead to individual patients.
- Patients that have registered an opt-out for scientific research are excluded

1. Introduction and rationale

The American Society of Anesthesiologists Physical Status (ASA-PS) classification system is a widely used tool for assessing surgical fitness and other clinical contexts. However, its inherent subjectivity and heavy reliance on clinician judgment can lead to inconsistencies in patient risk stratification, a critical component of perioperative care. Furthermore, the ASA-PS system has been adopted for various administrative and regulatory purposes beyond its original intent, such as quality assessment by the Dutch Health and Youth Care Inspectorate (IGJ), compensation decisions by private payers in the USA, patient triage, and determining suitability for certain types of surgery.

Given the broad and critical applications of the ASA-PS system, enhancing its precision and objectivity is of paramount importance. One way to achieve this is through the development of a machine learning algorithm that predicts ASA-PS based on preoperative variables. Anesthesiologists base the ASA-PS score on the presence of systemic diseases, which can be inferred from medication use. By leveraging data such as ATC codes, BMI, sex, age, routinely collected preoperative health data, and medication use, this algorithm could provide a more consistent and objective measure of ASA-PS.

This would not only improve clinical decision-making in patient risk stratification but also offer a more reliable tool for administrative and regulatory uses. Therefore, the development of such a machine learning tool presents a significant opportunity to advance both the science and practice of perioperative care. Incorporating medication use into the algorithm could further enhance its predictive power, as it is closely linked to systemic disease. This addition could help refine the ASA-PS classification, making it an even more valuable tool in the clinical setting.

2. Objective(s)

To develop a machine learning algorithm that can predict the American Society of Anesthesiologists Physical Score (ASA-PS) based on sex, BMI, age and medication use (ATC) and routinely collected preoperative health data and determine its performance.

3. Study type

3.1. Study type

- Retrospective
- Prospective
- Combination Retrospective/Prospective

3.2. Single center / Multicenter

- Single center
- Multicenter

3.3 Check all the applicable boxes

- Medical records (re-use of data from healthcare, including AI)
- Case report

- Re-use data from research
- Evaluations of quality of healthcare (retrospective)
- Research with additional use of residual material from regular healthcare
- Research with re-use of human material from research or existing biobank
- De novo biobank
- Phase IV research
- Healthcare evaluation research (prospective)
- Research with medical devices
- Research with In Vitro Diagnostic Tests
- Other research, describe

4. Study population

4.1. Study population

- Adults (16 years and older)
- Minors (younger than 16 years)
- Incapacitated adults (16 years and older)
- Incapacitated minors (younger than 16 years)

4.2. Population (base)

All patients who underwent a surgical, diagnostic or therapeutic procedure within the surgical suite of the Erasmus MC since 2018 (introduction new digital Hospital Information System, HiX) and who had a ASA-PS class recorded.

4.3. Inclusion criteria

In order to be eligible to participate in this study, a subject must meet all of the following criteria:

- Underwent a surgical, diagnostic or therapeutic procedure within the surgical suite of the Erasmus MC
- ASA score recorded in electronic medical record
- A verified medication list in HiX, or a filled out preoperative anesthesiological health questionnaire registered in HiX

4.4. Exclusion criteria

A potential subject who meets any of the following criteria will be excluded from participation in this study:

- Age <18 at moment of surgery
- ASA V-VI
- Opt-out registered in HiX

4.5. Sample size calculation

It is widely acknowledged that robust development and accurate validation of AI-based prediction models necessitate large sample sizes. (van Royen et al. EHJ 2023) However, no sample size calculators are currently available for development of AI models to perform a formal *a priori* sample size calculation.

Nevertheless, we used sample size guidelines for regression-based prediction models as a starting point (Riley et al., 2020). For an upper limit of the minimum required sample size (for a relatively unbalanced, multiclassification model) we used a c-statistic of 0.77 (Mudumbai et al., 2019) for a prediction of ASA I-IV, 302 candidate parameters, and a prevalence of 0.04 (for ASA IV, Model #10 in Table 1) and targeted a shrinkage of 0.9. This led to a sample size of 67,116.

For a lower limit of the minimum required sample size (for a more balanced, binary classification model) we used a c-statistic of 0.88 (Zhang et al., 2018) for a prediction of ASA I&II vs. III&IV, 302 candidate parameters, and a prevalence of 0.31 (for ASA III&IV, model #15 in Table 1), targeting a shrinkage of 0.9. This led to a sample size of 6,663.

Based on ratios observed in the dataset and an approximate size of the dataset of approximately 150,000 cases, we estimate approximately 30,000 to remain after applying inclusion and exclusion criteria for these specific models, satisfying at least the minimal criteria.

[figure not shown]
A larger sample size may be needed due to the higher complexity of AI-based prediction models, low prevalence (lower than 0.5) and expected high noise (van Royen et al. EHJ 2023). Therefore, a *posteriori* approach of plotting model errors against increasing sample percentages will also be used to justify the sample size (Rajput et al., 2023).

5.1. Research methods

Data collection: Health data obtained during the preoperative screening process for procedures registered in HiX from 2018-2023 will be extracted from the HiX database using a PowerBI query developed by ICON Healthcare in collaboration with the department of Anesthesiology under a data processing agreement. The patient ID's will be cross-referenced with the hospital's "opt-out" registry ("Baseline") and patients with an opt-out will be removed from the database. The resulting database will be stored on a secure, encrypted drive within DRE (Research environment) only available to the Principal Investigator. An extra Pseudonymized patient ID column will be added.

An extraction will then be performed of the following data: Pseudonymized patient ID, demographic information (sex, age), Body Mass Index (BMI), answers to questions in the standard anesthetic preoperative health questionnaire, medication use (represented by ATC codes), and ASA-PS scores. This resulting database will be used to construct the necessary datasets and be further preprocessed. (See DMP for further details).

Construction of data sets: all data will be processed according to the flow diagram in Figure 1. The split into a training and test set will be stratified on ASA-PS scores.

Data Preprocessing: The constructed (training and test) datasets data will be cleaned to handle missing values, outliers, and inconsistencies. Of patients that are present in the dataset with multiple procedures, procedures are first prioritized on the availability of both a verified medication list and a filled out preoperative health questionnaire, then the oldest record will selected and retained. Categorical variables, such as sex, will be encoded appropriately for the machine learning model. A variable on the total number of medication will be constructed. Other new features (variables) can be created based on existing data to improve the performance of our model (feature engineering). The exact nature of these new features is not predetermined, as they will be constructed based on the insights we gain during the exploratory data analysis and model training phases. Medication use will be recoded from the number of medicines a participant uses per ATC code, to the use of a medicine within a particular ATC code (yes/no). Variables will be normalized as required by the specific machine learning method.

Statistical Analysis and Model Validation: The development of a machine learning algorithm will be structured around the creation of predictive models using the H2O AutoML package, applicable in both Python and R environments. These models will undergo training on a meticulously preprocessed dataset, with a k-fold cross-validation strategy where 80% of the data is allocated for training purposes and the remaining 20% for validation. The primary outcome variable in focus is the ASA-PS score, with predictor variables encompassing age, sex, body mass index (BMI), responses to a health-related questionnaire, and ATC codes.

A suite of machine learning algorithms, bundled in the AutoML package, will be employed, including the Generalized Linear Model, Random Forest, Gradient Boosting Machine, and Deep Learning techniques. To enhance predictive performance, a Stacked Ensemble method, also known as Stacked Generalization, will be utilized to amalgamate the strengths of individual algorithms. The ensemble will be guided by a 'superlearner' or 'metalearner', with the Generalized Linear Model serving as the default choice.

Predictions for the response variable will be approached in two distinct manners:

1. A multiclass classification challenge, distinguishing between ASA scores I through IV.
2. A binary classification task, differentiating between the clinically significant groupings of ASA scores I&II and III&IV.

To tackle the multiclass classification, two primary strategies will be adopted:

1. The construction of a Multiclass Classification Ensemble, designed to model the ordinal ASA scores as a single entity.
2. The implementation of a Two-Stage One-vs-One Majority Voting scheme, where six binary ensemble models will be developed to discern between each pair of ASA scores. The collective output of these models will be synthesized through a majority voting mechanism, as facilitated by the diceR package in R.

The following combination of dependent variables (features) will be explored:

1. **Demographics and BMI only**
To evaluate the predictive power of base characteristics of patients.
2. **Medication combined with demographic data (age, gender) and BMI**
To evaluate the predictive power of a model based on medication and demographic data that should always be readily available.
3. **Health Questionnaire combined with demographic data (age, gender) and BMI.**
As 2, but answers to a general anesthetic health questionnaire instead of medication.
4. **Health Questionnaire and medication combined with demographic data (age, gender) and BMI.**
A combination of all above features.

This results in the following combinations of dependent (response) and dependent (predictor) variables:

Model	Dependent (response)	Independent (predictor)	Strategy
1	ASA 1 vs. 2 vs. 3 vs. 4	Demographics + BMI	Ensemble (multiclass)
2	ASA 1 vs. 2 vs. 3 vs. 4	Demographics + BMI	Two-stage OVO-Majority voting
3	ASA 1 vs. 2 vs. 3 vs. 4	Model 1 + Medication	Ensemble (multiclass)
4	ASA 1 vs. 2 vs. 3 vs. 4	Model 2 + Medication	Two-stage OVO-Majority voting
5	ASA 1 vs. 2 vs. 3 vs. 4	Model 1 + Questionnaire	Ensemble (multiclass)
6	ASA 1 vs. 2 vs. 3 vs. 4	Model 2 + Questionnaire	Two-stage OVO-Majority voting
7	ASA 1 vs. 2 vs. 3 vs. 4	Model 1 + Medication + Questionnaire	Ensemble (multiclass)
8	ASA 1 vs. 2 vs. 3 vs. 4	Model 2 + Medication + Questionnaire	Two-stage OVO-Majority voting
9	ASA 1 & 2 vs. 3 & 4	Demographics + BMI	Ensemble (binary)
10	ASA 1 & 2 vs. 3 & 4	Model 9 + Medication	Ensemble (binary)
11	ASA 1 & 2 vs. 3 & 4	Model 9 + Questionnaire	Ensemble (binary)
12	ASA 1 & 2 vs. 3 & 4	Model 9 + Medication + Questionnaire	Ensemble (binary)

Model development process is inherently iterative, commencing with the aforementioned methodologies. As the project progresses, the pursuit of the most efficacious model will lead to the exploration of additional refinements following the initial model constructions. Examples of possible refinements are: dimensionality reduction, dataset balancing, the modeling of data subsets, the incorporation of domain knowledge leading to the creation of more sophisticated features, and the identification of independent variables that may suffer from the perfect separation problem. This comprehensive approach ensures a robust and systematic development of a machine learning algorithm tailored to the specificities of the ASA-PS score prediction.

Validation: The models will be validated using a separate holdout test set (10% of original dataset). This will ensure that our models generalize well to unseen data. The validation process

will involve applying the models to the test set and comparing the predicted outcomes with the actual outcomes.

Model Evaluation: The performance of the models will be evaluated using metrics such as accuracy, precision, recall, AUC and F1-score. Confusion matrices and ROC's will be used to visualize the performance of our models. Misclassifications will be manually reviewed to gain qualitative insights into the model's performance, with special emphasis on "catastrophic error examples", e.g. ASA I instead of IV, or ASA IV instead of I.

SHAP (Shapley Additive exPlanations) and LIME (Local Interpretable Model-agnostic Explanations) will be explored as techniques for interpreting the models. The calibration of the models will be evaluated using calibration plots. The optimal method for a priori sample size calculation in machine learning algorithms lacks consensus. Consequently, we will utilize the entire available dataset and conduct a post hoc assessment by plotting model errors against increasing sample percentages (Rajput et al., 2023). To detect possible bias in the final model, the 'fairness' of the model will be assessed from different perspectives for different subpopulations.

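### As Section 5.1 is written, one record per patient is selected after the training/test split, so a repeat patient can be in both training and holdout

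*Combined protocol and SAP*

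**What the plan says.** Section 5.1 of the combined protocol and SAP describes the steps in this order.

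- **Data collection.** After extraction: "This resulting database will be used to construct the necessary datasets and be further preprocessed". Section 9.1 repeats the sentence.
- **Construction of data sets.** The text refers to a diagram: "all data will be processed according to the flow diagram in Figure 1". It then gives the split rule: "The split into a training and test set will be stratified on ASA-PS scores". No other stratification or grouping variable is named.
- **Data Preprocessing.** The paragraph opens: "The constructed (training and test) datasets data will be cleaned to handle missing values, outliers, and inconsistencies". Its next sentence is the one-record rule. It begins "Of patients that are present in the dataset with multiple procedures", gives priority to procedures with both a verified medication list and a completed questionnaire, and ends "then the oldest record will selected and retained".
- **Validation.** "The models will be validated using a separate holdout test set (10% of original dataset"), followed by the stated purpose: "This will ensure that our models generalize well to unseen data".

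The inclusion and exclusion criteria in Sections 4.3 and 4.4 do not contain the one-record rule, so nothing there applies it earlier.

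**The concern.** The split comes first in the text, and the one-record rule sits in a step that acts on the sets the split has produced. Someone programming in that order would split procedures and then reduce each set to one record per patient. A patient operated on more than once could then supply one training record and one holdout record.

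Such a patient is not unseen. Sex is the same, and age, BMI, medication, questionnaire answers and ASA class will often be similar. The planned learners include random forests, gradient boosting and deep learning, which are flexible enough to exploit that similarity. The holdout is the only separate test set described, so optimism there would carry into the reported performance of all twelve models.

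The risk is confined to training versus holdout. With the rule run inside the training set, each patient has one training record, so the cross-validation folds cannot share patients.

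**Working it through.** The plan states no figure for overlap, so there is none to reproduce. The check is whether the text allows overlap and, if so, how much.

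**Inputs**

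- Holdout share: 10% (Section 5.1, Validation).
- Unit of the split: taken as the procedure, because the text names no grouping by patient. This is the reading under test.
- One-record rule run inside each set. This is also part of the reading under test.
- Repeat rate among eligible patients: not in the documents, so a range is assumed below.

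**One patient with n eligible procedures**

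Each procedure goes to the holdout with probability 0.1.

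- P(in holdout) = 1 − 0.9ⁿ
- P(in both sets) = 1 − 0.9ⁿ − 0.1ⁿ
- P(training record, given in holdout) = the second divided by the first

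| n | P(in holdout) | P(in both) | P(training record, given in holdout) |
|---|---|---|---|
| 2 | 1 − 0.81 = 0.19 | 1 − 0.81 − 0.01 = 0.18 | 0.18/0.19 = 0.947 |
| 3 | 1 − 0.729 = 0.271 | 1 − 0.729 − 0.001 = 0.27 | 0.27/0.271 = 0.996 |

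These figures need no repeat rate.

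**Share of holdout patients affected**

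Let a share p of eligible patients have exactly two procedures and the rest one. The share of holdout patients who also have a training record is

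0.18p / [0.1(1 − p) + 0.19p]

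| p (assumed) | Calculation | Share affected |
|---|---|---|
| 2% | 0.0036/0.1018 | 3.5% |
| 5% | 0.0090/0.1045 | 8.6% |
| 10% | 0.0180/0.1090 | 16.5% |
| 20% | 0.0360/0.1180 | 30.5% |

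A simulation with an exact 10% draw in each ASA stratum (27,000 patients, an assumed ASA mix) agreed with the formula to within 0.3 percentage points. Stratifying on ASA-PS therefore does not remove the overlap.

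**The safe orders**

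If the rule is run on the whole file, before or after the split, each patient has one record in total and the overlap is 0. A split grouped by patient ID also gives 0. The simulation of whole-file selection found no overlapping patients.

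**Are repeats likely?**

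The rule itself expects patients with several procedures. Section 4.5 gives about 150,000 cases and the Summary gives more than 90,000 patients: 150,000/90,000 = 1.67 procedures per patient at most, since the patient count is a lower bound. Both counts precede eligibility, which Section 4.5 expects to leave about 30,000 for the models considered there, and they may describe different populations. The ratio shows only that repeats may be common; it does not give p.

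**The case against.** The strongest reply is that the order may be settled in places not available for this review. Section 5.1 says Figure 1 governs the processing and refers to the data management plan for detail. An unseen figure is not a gap in the plan.

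The wording also supports a safe reading. The sentence on the constructed sets concerns missing values, outliers and inconsistencies. The one-record rule is a separate sentence, speaks of one dataset in the singular, and keeps a single oldest record. Run inside each set, it would leave some patients with two records, which defeats its evident purpose. The construct-then-preprocess sentence in Sections 5.1 and 9.1 is one text used twice, and the datasets it mentions could be the different feature sets. Finally, the repeat rates are assumed, and no effect on AUC or accuracy is shown.

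Much of this stands. The safe reading is possible, the repeated sentence is weak support, and the effect on performance cannot be computed from the documents. But the rule directly follows a sentence about training and test sets already built, the holdout is defined as 10% of the original dataset, and no visible sentence requires separation by patient. Calling the holdout separate and the data unseen states an aim; separate records can still belong to the same patient. Both readings remain open, and one of them undermines the holdout.

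**Conclusion.** The concern holds, as a condition rather than a proven leak. Followed in the order written, with the rule run inside each set, Section 5.1 lets the same patient contribute to training and to the only holdout, and the bias would tend to be optimistic. A patient with two eligible procedures who is in the holdout would almost always (95%) have a training record too. The overall share affected depends on a repeat rate the documents do not give: 3.5% to 30.5% for assumed rates of 2% to 20% with exactly two procedures, and 0% if the rule is run on the whole file. The size of any bias in AUC or accuracy is unknown. The point should be settled before the models are built. Confidence is medium, because Figure 1 or the data management plan may already fix the safe order.

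**What to change.** In Section 5.1, move the existing record-selection rule ahead of the split: apply it to the full eligible dataset by pseudonymised patient ID, then make the ASA-stratified 90/10 split. Splitting by patient ID would serve equally well. Add one sentence: *No patient ID is in both the training and the test set.* If Figure 1 or the data management plan already shows this order, only the text of Section 5.1 needs aligning with it.

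Section 9.2 says patient IDs are deterministically encrypted before further preprocessing, so the same patient always has the same code. Both the selection and a count of IDs common to the two sets (expected: zero) can be done with the data already planned.

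The cost is a change of protocol wording and possibly the order of two programming steps, with no new data. If the unsafe order had been intended, reported holdout performance may be lower after the change, by an amount that cannot be stated in advance.

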9.2 Privacy protection

Describe how subject's privacy is protected. Describe how, when and by whom data is coded (unique code without initials or date of birth) and how the key table is safeguarded, mention the General Data Protection Regulation.

Please note: The handling of personal data has to comply with the EU General Data Protection Regulation and the Dutch Act on Implementation of the General Data Protection Regulation (in Dutch: Algemene Verordening Gegevensbescherming en Uitvoeringswet Algemene Verordening Gegevensbescherming).

Before further preprocessing the data is stored on an encrypted, secure location in a DRE Workspace. There, patient hospital IDs (PID) are deterministically encrypted using encryption packages in R. The key is stored on a separate password protected location within Microsoft Azure only available to the principal investigator. Age at the time of the preoperative screening is calculated using the birth date and date of the preoperative screening. Only 'age' is used for further analyses. All other data is not traceable to individual patients.

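### A 10% holdout from the same hospital and the same years estimates internal performance only; it cannot ensure generalization, and no planned evaluation looks at calendar time or another centre

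*Combined protocol and SAP*

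**What the plan says.** All references are to the combined protocol and SAP.

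- **Validation (5.1).** The models are applied to a separate holdout of 10% of the original dataset, and predicted and actual ASA-PS are compared. The plan concludes: "This will ensure that our models generalize well to unseen data".
- **Split (5.1, construction of data sets).** "The split into a training and test set will be stratified on ASA-PS scores". No rule by date or by site is stated. The section refers to a flow diagram (Figure 1) that is not visible in the text available for review.
- **Period and centre.** The data are from "procedures registered in HiX from 2018-2023" (5.1), for procedures "within the surgical suite of the Erasmus MC since 2018" (4.2). The tick box in 3.2 cannot be read, but no other hospital is named.
- **Variables.** The analysis extract holds a pseudonymized ID, sex, age, BMI, "answers to questions in the standard anesthetic preoperative health questionnaire, medication use (represented by ATC codes), and ASA-PS scores" (5.1, repeated in 9.1). No date is listed. Section 9.2 calculates age from birth date and screening date, and then states: "Only 'age' is used for further analyses".
- **Purpose.** The Summary, in its justification for the consent exception, gives triage for preoperative screening as the general purpose. The rationale also foresees administrative and regulatory use.

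**The concern.** The sentence credits the design with a property it does not have. A held-out tenth of the same records is a sound check on overfitting. It says nothing direct about patients seen after 2023 or in other hospitals, and those are the patients for whom a triage tool would be used.

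Drift is plausible on the plan's own account. Section 1 calls the ASA-PS subjective and dependent on clinician judgment, and 7.1 says that the label is assigned in routine care by anesthesiologists or residents. Plausible is not shown: the documents contain no evidence that labelling, questionnaire use or medication recording changed. At stake is therefore the conclusion on generalization, which the planned analyses would leave unsupported. Building the models and estimating their internal performance are not affected.

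**Working it through.** The challenged sentence carries no figure to reproduce. The sample sizes in 4.5 concern development and do not bear on this point.

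**Inputs from the documents.** Holdout share 10% (5.1); about 30,000 cases expected for the models considered in 4.5, from about 150,000; prevalence 0.04 for ASA IV and 0.31 for ASA III and IV; c-statistic 0.88 for the binary model (4.5).

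**Step 1. Does another evaluation fill the gap?**

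| Planned evaluation (5.1, 7.2, 7.4) | Calendar period? | Other centre? |
|---|---|---|
| Accuracy, precision, recall, F1, AUC | not named | not named |
| Calibration plots | not named | not named |
| Review of misclassifications | not named | not named |
| SHAP, LIME | not named | not named |
| Learning curves by sample size | not named | not named |
| Fairness by subpopulation | not named | not named |

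None does.

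**Step 2. Is stratification the cause?** With 30,000 cases the holdout has 3,000 and training has 27,000. For an unstratified random split, the 95% range of the difference in class share between the two sets is ±1.96 × √[p(1−p)(1/3,000 + 1/27,000)].

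- p = 0.31: 1.96 × 0.0089 = 1.7 points.
- p = 0.04: 1.96 × 0.0038 = 0.7 points.

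The class shares would nearly match without stratification. What removes the information on drift is that the test set is not separated in time.

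**Step 3. What would each split show if drift were present?** The drift values below are assumptions; the documents give none.

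(a) *Change in class share.* Let the ASA III and IV share be 0.31 + D(t − 0.5), with t running from 0 to 1 and equal volume over time. The first 90% has mean t = 0.45 and the last 10% has mean t = 0.95, so the gap is 0.5 × D. For D = 3, 6 or 10 points the gap is 1.5, 3.0 or 5.0 points in a latest-10% test and 0 in an ASA-stratified split. This is a gap in class share, not a calibration error. If the predictors carry the change, mean predicted risk moves with it.

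(b) *Change in labelling at fixed predictors.* The linear predictor is a + d·x, with d = √2 × z(0.88) and a = ln(0.31/0.69) − d²/2. A shift is added linearly over the period, the intercept is set on the training part, and observed/expected is taken in the test part (simulation).

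| Assumed shift over the period (logits) | Holdout spread over all years | Latest 10% |
|---|---|---|
| 0 | 1.00 | 1.00 |
| 0.1 | 1.00 | 1.02 |
| 0.25 | 1.00 | 1.05 |
| 0.5 | 1.00 | 1.10 |
| 1.0 | 1.00 | 1.21 |

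**Step 4. Could a latest-period test see this?** The latest 10% of 30,000 is 3,000 records. The binomial 95% half-width at a share of 0.31 is 1.96 × √(0.31 × 0.69/3,000) = 1.7 points, or 1.7/31 = about 5% on the observed/expected scale. A ratio of 1.10 would show, 1.05 would be borderline and 1.02 would not. At 4% there would be 3,000 × 0.04 = 120 ASA IV cases. A recall of 0.5 then has a half-width of 1.96 × √(0.25/120) = 8.9 points, so ASA IV results would be descriptive.

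**Step 5. Is the date available?** It must exist at some stage: 9.2 uses the screening date to calculate age, and 5.1 needs time order to keep the oldest record of a patient. The listed extract does not carry it forward, so performance by period could not be examined in the analysis dataset as described.

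**The case against.** The strongest reply is that in machine learning, unseen data ordinarily means records not used in training. On that reading the sentence claims only what a holdout delivers. The stated objective is to develop an algorithm and determine its performance, not to show stability over time, and a held-out test set is accepted internal validation for a development study. The triage purpose stands in the consent justification and not in the objective. This much stands: the holdout is a legitimate main test and should be kept. It does not rescue the verb, since a test set estimates performance and ensures nothing, and the rationale looks to clinical and regulatory use.

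A reader might also infer several stronger things that the documents do not support.

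- *That the split is random.* The text never says so, and Figure 1 is not shown. It is the likely reading, because only ASA-PS is named and no date is listed.
- *That stratifying on ASA-PS conceals drift.* Step 2 shows that it adds little, and it protects the small ASA IV class. Exact equality of class shares is not secure either: record selection is described after the split, and balancing the data is a possible refinement.
- *That a rise in the ASA III and IV share of a few points makes the model wrong by as many points.* That holds only if the predictors explain none of the rise.
- *That a test on 2023 alone should replace the holdout.* An even one-sixth (30,000/6 = 5,000 records) ignores the oldest-record rule. Among equally complete records, a patient returning in 2023 is represented by an earlier one. Late years therefore hold fewer and mostly first-time patients, and a difference there may reflect selection as well as drift.

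**Conclusion.** The point holds in a limited form. The planned holdout, as described, estimates performance in the same centre and period. It cannot ensure generalization to later patients or other hospitals, it would not reveal drift if present, and nothing else in the plan tests this. The conclusion rests on the stated split having no date or site rule; a rule of that kind in Figure 1 would change it.

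No size of error can be given, because the documents contain no drift data. The ratios of 1.00 to 1.21 in the working only show what the present design could not detect under assumed shifts. The holdout size also depends on reading: 10% of about 30,000 is 3,000, but if the original dataset means the roughly 150,000 cases it is 15,000, with about 600 ASA IV at 4%. Neither reading affects the conclusion.

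This is not a flaw in model building. It is an unsupported claim, and an inexpensive addition would let the study say something about stability over time.

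**What to change.** 1. Replace the sentence in 5.1 with: *The holdout estimates internal performance in the same centre and period; external validity is not tested.* State in the text how the split is drawn.
2. Keep procedure year in the pseudonymized extract (5.1 and 9.1) and update the privacy text in 9.2 to match.
3. Keep the planned holdout as the main test and add a secondary temporal validation. Refit the final pipeline on the earlier years and test it once on the latest period, for example the last year or the latest 10% of records, with no patient in both parts. Report discrimination and calibration there.
4. Report the number of records and the case mix of the latest period beside these results, and say that differences may reflect patient selection as well as drift. Say also that feature choices made on all years will already have drawn on late records, so the result may be somewhat favourable.
5. If the temporal test is not added, list its absence as a limitation.

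The cost is one more field in the extract and the privacy description, a possible amendment to the review committee (section 12), one extra model fit, and reported performance that may be slightly lower. Validity in other hospitals would remain untested.
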